Title: Intradiscal Platelet-Rich Plasma Injection for Chronic Discogenic Low Back Pain

Primary Investigator: [name], [name], DO

Objectives:

To assess changes in pain, physical function, health-related quality of life and cost-effectiveness in patients with discogenic low back pain after an intradiscal injection of PRP.

Introduction

Low back pain is one of a few conditions which affects all individuals through the lifespan. The etiology of low back pain is multifactorial and in many cases self-limiting, however it also is the leading cause for working age adults to be disabled with more than \$87 billion spent on low back pain disorders in 2013¹. Lumbar disc herniation and internal disc disruption are two causes more common in these younger age groups² reaching 39-42% with a predicted probability above 60% until age 50y. While the natural history of disc herniation suggests most individuals will return to a prior level of function in 3-6 months, there is a high rate of recurrent episodes which can cause short-term disability. Continued pain from a discogenic source can lead to decreased activity levels and accelerate degenerative changes in the disc and facet joints as described by Kirkaldy-Willis.

Current guidelines for treatment of axial low back pain from discogenic sources including those with radiculopathy include a 6-12-week course of conservative care including medications, therapy, acupuncture, chiropractic and exercise before an interventional paradigm of injections and/or surgical treatment. For those individuals who do not improve with conservative care and have predominately axial pain, options are limited as success rates from epidural steroid injections and surgery are 50% or less. Other treatments include chymopapain injection, intradiscal electrothermal annuloplasty (IDET), nucleoplasty, methylene blue injection^{3,4}, ozone injection⁵, fibrin sealant injections⁶. All of which have 50% or less likelihood of reducing pain more than 50%, although much of this data is from uncontrolled or prospective case-control studies only.

Platelet- rich plasma (PRP) injections stand apart from those listed above in that they are purported to be “regenerative” interventions for the diseased lumbar disc. PRP is a concentrated injectant of growth factors and anabolic factors which have in vitro and animal studies that have demonstrated upregulated proteoglycan synthesis and nucleus pulposus proliferation, restoration of disc height, healing of annular puncture wounds and anti-inflammatory effect with down regulation of TNF-alpha and IL-1.⁷ There has been limited clinical trials in humans on the effect of intradiscal PRP, including 3 trials of which 1 is a RCT and 2 are prospective series. Efficacy of intra-discal injection has shown statistically significant benefits in reduction in pain, improvement in physical function at follow-up points from 3-24 months. Each of these trials have limited sample sizes, short duration follow-up and lack of a standardized PRP preparation, making the generalizability difficult.

Subjects

A total of 100 subjects, aged >18 years old on the day of enrollment, will be recruited for participation in this study.

De-identification

All subjects will be assigned a unique alphanumeric identifier. No personally identifiable information will be used in the final database. All data will be stored on a highly secure, password protected computer.

Participant Recruitment

Our intended subject demographic includes an active population between the ages of 18 and 80 years on the day of enrollment. We intend to recruit participants primarily through word-of-mouth. Additionally, recruiting will take place through the distribution of flyers to the Health Sciences Education Building, University of Utah Student Life Center, the University of Utah Orthopaedic Center, and the University of Utah hospital. Upon first contact with the potential participant, the study coordinator or research associate will provide a basic description of the study and review inclusion and exclusion criteria and discuss general health status. Interested volunteers who qualify will be asked to report to the University of Utah Orthopaedic Center. Prior to screening procedures and after being informed of any potential risks involved in the study, volunteers will be asked to provide written, informed consent for study participation.

Inclusion Criteria:

- 1) Age greater than 18 years of age at day of enrollment.
- 2) Clinical diagnosis of refractory discogenic low back pain for >3 months.
- 3) Magnetic resonance imaging pathology consistent with clinical symptoms/signs or positive lumbar provocative discography according to SIS/IASP standards at one or two levels.
- 4) Back pain greater than leg pain with an intensity of at least 4/10 or higher using the Numerical Rating Scale (NRS).
- 5) Pain duration of more than 12 weeks despite trial of conservative therapy (medications, physical therapy, or chiropractic care) for 2 months.

Exclusion criteria:

- 1) Refusal to participate, provide consent, or provide follow-up information for the 24-month duration of the study.
- 2) Contraindications to intradiscal injection of PRP (active infection, bleeding disorders, current anticoagulant or antiplatelet medication use, allergy to iodinated contrast, penicillin or clindamycin and pregnancy or breastfeeding).
- 3) More than 2 levels of clinical or discogram proven pain.
- 4) Non-discogenic source of low back pain as identified by separate diagnostic blocks.
- 5) Negative lumbar provocation discography.
- 6) Active moderate to severe lumbar radiculopathy.
- 7) Intradural disc herniation.
- 8) Spinal fracture within the past 6 months.
- 9) Steroid injection in the spine within the last 30 days.
- 10) Any intradiscal injection other than contrast dye or anesthetic in the last 30 days.
- 11) Prior fusion at level considered to be the source of the pain.
- 12) Prior lumbar spine surgery within the last 6 months.
- 13) AP diameter of spinal canal less than or equal to 9mm at level to be treated.
- 14) Severe uncontrolled medical condition.
- 15) Moderate to severe hepatic dysfunction.
- 16) Severe psychological illness.
- 17) History of Inflammatory arthritis.
- 18) Malignancy within past 5 years except basal cell or squamous cell skin cancer.
- 19) Current use of equal to greater than 30mg morphine-equivalent per day of opioid use.
- 20) A history of alcohol or drug abuse within past 5 years.

- 21) Use of any investigational drug within past 30 days.
- 22) A known allergy or sensitivity to citrate (used for processing PRP).
- 23) Severe anaphylactic/anaphylactoid reaction to any medications used.
- 24) Pending litigation involving subject's back pain.
- 25) No insurance coverage for any subsequent tests or procedures.
- 26) Disc protrusion greater than 5mm from base of vertebral body.
- 27) Greater than 50% disc height loss at involved level(s).
- 28) Inability or unwillingness to continue rehabilitation protocols.

Study design:

Survey/Questionnaire research

Observational research

Prospective Clinical Research

Power Analysis

Size of study groups: 100 total participants.

Procedures:

All visits are standard of care, however completion of questionnaires will be for study purposes in follow-up clinic visits and at specified time-frames. Study involvement includes the following visits:

Screening: Questionnaires and clinical examination

Enrollment: Questionnaire and clinical examination

Follow-up:

- 1 month post-injection- questionnaires and clinical exam
- 2 months post-injection- questionnaire and clinical exam
- 3 months post-injection- questionnaire and clinical exam
- 6 months post-injection- questionnaire and clinical exam
- 9 months post-injection- questionnaire and clinical exam
- 12 months post-injection- questionnaire and clinical exam
- 24 months post-injection- questionnaire and clinical exam
- 36 months post-injection- questionnaire and clinical exam

Questionnaires: Demographics, medication use (MSQ III), ODI, PROMIS PF CAT, PROMIS Global 10, NRS for back and leg pain (current, average last week), PGIC score, PSQ-3, and patient satisfaction with treatment score (5 point: 1, very dissatisfied; 2, dissatisfied; 3, neither satisfied nor dissatisfied; 4, satisfied; and 5, very satisfied).

Data Collection:

An electronic data collection sheet (via iPad) will be used to record all pre-procedure data (see data collection sheet):

- 1) Age (years).
- 2) Sex.
- 3) Height (cm).
- 4) Weight (Kg).
- 5) Duration of pain (weeks).

6) Radiologic diagnosis based on MRI of the Lumbar Spine.
7) NRS for pain; separate scores for back pain and for leg pain

- 8) Oswestry Disability Index (ODI)
- 9) PROMIS Physical Function scale version 2
- 10) PROMIS Global 10
- 11) Medication Quantification Scale (MQS III) score
- 12) Daily opioid use in morphine equivalents

Additional questions for post procedure survey

- 13) Patient Global Impression of Change (PGIC)
- 14) Patient satisfaction score (five-point Likert scale: 1, very dissatisfied; 2, dissatisfied; 3, neither satisfied nor dissatisfied; 4, satisfied; and 5, very satisfied)

Immediately after injection the following will be obtained:

- 15) Fluoroscopy time
- 16) Post-injection NRS pain score; separate scores for back pain and for leg pain
- 17) Adverse events, if they occurred

Data Storage:

Hard copy data will be collected and stored in a password-protected computer located in the Division of PM&R. Participants will each be assigned an ID number that will be used as the sole identifier on any documents. Participant data will be compiled onto a single password protected file, where they will only be identified by their ID number. An enrollment log will be the only file where subject names are correlated with ID numbers. This will be kept in a separate, secure, password-protected file in the Division of PM&R.

Data Analysis Plan

The primary outcome will be the proportion of participants with >80% and >50% reduction in back pain on the NRS pain score at the 2-month follow-up assessment. Secondary outcomes included reduction in median NRS pain score, ODI, change in PROMIS PF-CAT, MQS III, opioid consumption in daily morphine equivalents, PGIC score, PSQ-3, and satisfaction score. Secondary outcomes will also be defined based on categorical “responder analysis” definitions of important clinical change given the National Institutes of Health recommendation for responder analysis in the assessment of therapeutic spine pain interventions. The responder analysis will include the proportion of patients with 30% or greater improvement on the ODI, a PGIC score less than 3 (indicating “improved” or “very much improved”), a 6.8 or greater point reduction on the MQS III score (equivalent to approximately 10 daily morphine equivalents), and the proportion of participants who undergo surgical spine surgery in the study period.

Statistical analysis

Means and standard deviations of subject demographic data, as well as pain, functional, and treatment satisfaction scores will be calculated. Intergroup differences will be assessed by t test for numerical data and Chi Square or Fisher Exact test for categorical data. Regression modeling will be implemented using ANOVA to assess for patient traits and characteristics that increase the likelihood of efficacy using one technique as opposed to the other.

Risks/Benefits:

Risks of study participation are the same as those for any standard fluoroscopically guided lumbar intradiscal injection performed in the PM&R Spine Clinic. These include: local infection, intradiscal infection (discitis), epidural hematoma or abscess, dural puncture and potential post-dural puncture headache, paresthesia during needle placement, pain at the injection site, failure to relieve pain, allergic reaction to products or medications being used. Utilizing fluoroscopy, the risk of nerve damage, spinal cord injury or intravascular injection is less than 1:500,000. The length of stay and length of recovery is no longer than that of a standard spinal injection performed in the PM&R Spine Clinic at present.

There are no direct benefits to the individual by participating in this study. The patients will be presented with the same options of treatment whether they enroll in the study or decide not to. The information extracted from this study may provide the investigators a better understanding of a patient's short and long-term pain response and physical function following a intradiscal PRP injection.

Study Termination Criteria

- Adverse events considered/identified by the medical staff during the procedure process
- The subject requests to be withdrawn from the study during the procedure.

Safety Monitoring Plan

Safety will be monitored by all members of the study team:

[name]

[name], DO

The Principal Investigator is a physician at the University of Utah Health Sciences Center. Members of the data and safety monitoring committee will be in close contact with all the subjects throughout the study, both in-person and via telephone. The members of the data and safety monitoring committee will review potential side effects and adverse reactions with each subject at the time of delivery of the study drug and at the time of each sample collection. All the committee members are located at the University of Utah Orthopaedic Center; all members have research experience.

References

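### Adverse events have a specified data item only immediately after the injection; no follow-up visit has a field for later harms and no summary of harms is planned

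*Combined protocol and SAP*

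**What the plan says.** All references are to the combined protocol and SAP.

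- **Data Collection.** Under "Immediately after injection the following will be obtained" come three items: fluoroscopy time, a post-injection pain score, and item 17, "Adverse events, if they occurred". No other item in the numbered list concerns adverse events. The two questions added for the post-procedure survey are global impression of change and satisfaction. The section also says "An electronic data collection sheet (via iPad) will be used to record all pre-procedure data", and points to a sheet that is not among the supplied documents.
- **Procedures.** There are eight follow-up visits, from "1 month post-injection- questionnaires and clinical exam" to "36 months post-injection- questionnaire and clinical exam". The instruments begin "Questionnaires: Demographics, medication use (MSQ III), ODI, PROMIS PF CAT, PROMIS Global 10, NRS for back and leg pain" and go on to global impression of change, PSQ-3 and satisfaction.
- **Safety Monitoring Plan.** Committee members are to stay in touch with participants for the whole study, face to face and by telephone. They are to go over side effects with each participant "at the time of delivery of the study drug and at the time of each sample collection".
- **Risks/Benefits.** The listed risks include discitis, epidural hematoma or abscess, and post-dural puncture headache.
- **Data Analysis Plan and Statistical analysis.** Summaries are planned for demographics, pain, function and satisfaction, together with responder proportions and the proportion having spine surgery. Adverse events are not mentioned.

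**The concern.** The one moment at which the plan specifies that adverse events become study data is the moment at which several of the listed harms are least likely to be visible. The documents give no onset times. As a general assumption, an infection introduced by a needle would not ordinarily show itself straight after the injection, and a post-dural puncture headache need not.

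Without a recording step at follow-up, whether a later harm reaches the database depends on who asked, what was written in the clinic note, and whether anyone carried it across. That can differ between participants. The eventual report might then state few or no adverse events after an intradiscal injection in 100 people, and a reader could not tell whether that describes the follow-up period or only the procedure room.

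**Working it through.** No figure in the plan is in dispute, so there is nothing to reproduce. The check sets the sections side by side, followed by an illustration on stated assumptions.

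**Step 1: is there a recording point after the injection day?** The visits are at 1, 2, 3, 6, 9, 12, 24 and 36 months, which is 8. Visits with a specified adverse-event item: 0 of 8. Listed questionnaires that are adverse-event instruments: none. The first scheduled contact after item 17 is at 1 month.

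**Step 2: does the Safety Monitoring Plan supply one?** No sample collection appears in the visit schedule. Two readings are plausible:

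| Reading of sample collection | Does review reach follow-up? | Is a field specified to record it? |
|---|---|---|
| Blood draw for PRP | No | Item 17 only |
| Slip for data collection | Yes, at the visits | No |

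The text does not settle which is meant. Under either reading, uniform recording of later harms is unspecified.

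**Step 3: is there a planned summary?** None, not even of item 17. The nearest outcome is spine surgery, counted in the responder analysis. It does not separate a harm of the injection from failure to relieve pain, and it misses harms treated without surgery.

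**Step 4: what incomplete capture does to interpretation (illustration).** Assume a true rate p of a delayed harm and a fraction c of such events that reaches the data. Neither is given in the documents. With n = 100, the chance of recording at least one event is 1 − (1 − pc)^100:

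| p | c = 1 | c = 0.5 | c = 0 |
|---|---|---|---|
| 0.5% | 39.4% | 22.1% | 0% |
| 1% | 63.4% | 39.4% | 0% |
| 2% | 86.7% | 63.4% | 0% |
| 3% | 95.2% | 77.9% | 0% |

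Zero events in 100 gives a one-sided 95% upper bound of 1 − 0.05^(1/100) = 2.95%, but only if c = 1 for everyone.

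**Step 5: the denominator matters to the remedy.** The two-sided exact 95% upper limit for zero events is 1 − 0.025^(1/n). For n = 100 it is 3.6%. If 30 participants were lost (an assumed figure), the 70 actually assessed give 1 − 0.025^(1/70) = 5.1%. Keeping lost participants in the denominator treats them as event-free and makes the limit look better than the data allow.

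**The case against.** The strongest reply is that the plan provides more follow-up for safety than item 17 suggests. There are eight clinical examinations, and a committee commits to continuing contact and to asking each participant about side effects. If sample collection is a slip for data collection, that review already takes place at every visit. The data collection sheet is not supplied. Although it is introduced as recording pre-procedure data, the numbered list under the same heading runs on to post-procedure items, so the sheet may hold more than its description says. The list is also not exhaustive, since spine surgery is analysed but not itemised. Finally, the study describes itself as observational and survey research with standard-of-care visits, and safety is not among its objectives.

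Much of this stands. A reader might infer that later harms would go undetected or certainly unrecorded, or that there is no safety follow-up at all. The documents do not support that: the examinations and the contact commitment give real opportunity for detection. What they lack is a schedule, a form and a recording rule for the result, so the gap is one of recording and reporting. Safety not being an objective limits the weight of the point. It does not remove it, because the plan chose to collect adverse events and to monitor safety.

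A reader might also cite the stated duration, "provide follow-up information for the 24-month duration of the study", against the 36-month visit as further support. That is a separate inconsistency. It affects every outcome and should be reconciled, but it says nothing about whether adverse events are recorded.

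**Conclusion.** The point holds as a gap in specified recording and reporting. One adverse-event item is timed at the injection, 0 of 8 follow-up visits has one, no summary is planned, and the only stated trigger for further review is an undefined term. Followed as written, delayed harms from the plan's own risk list would not enter the study data uniformly, and a low or zero count could not be taken to cover them.

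The number of events that might be missed cannot be estimated, because the documents give neither event rates nor capture. The percentages in the working show only how interpretation depends on capture. Confidence is moderate, since the unsupplied sheet could contain a follow-up field and the intended meaning of sample collection is open. The primary outcome at 2 months is unaffected. The change should be made, but the pain and function analyses do not depend on it.

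**What to change.** 1. **Data Collection and Procedures.** Add to the form at each existing follow-up visit an item on adverse events since the last contact: yes or no and, if yes, type, onset date, seriousness and relation to the injection. Name the harms listed under Risks/Benefits as specific prompts, so that the answers isolate the events of interest from unrelated illness.
2. **Safety Monitoring Plan.** Define sample collection, and state that adverse events are reviewed at each scheduled follow-up visit.
3. **Data Analysis Plan.** Add a descriptive table of participants with any, any serious, and any injection-related adverse event, and with each harm listed under Risks/Benefits. Give exact 95% confidence intervals by visit window among participants actually assessed in that window. Report the number injected and the number lost alongside, and do not count lost participants as event-free. No new hypothesis or objective is needed.

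**Cost.** At most 100 × 8 = 800 yes/no answers at visits that already include questionnaires and an examination, with detail fields only for a yes. Beyond that, one definition, one sentence on review times and one table. The downside is slightly longer visits, some data entry, and a judgement of seriousness and relatedness for each reported event.

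Separately, the 24-month duration in exclusion criterion 1 and the 36-month visit need to be reconciled.

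### Do two unranked responder cut-offs, with no named NRS version or baseline visit, leave the primary outcome unsound?

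*Combined protocol and SAP*

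**What the plan says.** The Data Analysis Plan gives the primary outcome in one sentence: "The primary outcome will be the proportion of participants with >80% and >50% reduction in back pain on the NRS pain score". The same sentence fixes the time, since it is the "reduction in back pain on the NRS pain score at the 2-month follow-up assessment". The site (back), the time (2 months) and both cut-offs are therefore set in advance. The sentence does not order the cut-offs or attach a success rule.

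Two details are left open:

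- **NRS version.** The questionnaire list under Procedures has "NRS for back and leg pain (current, average last week". Item 7 of the pre-procedure list under Data Collection has "NRS for pain; separate scores for back pain and for leg pain", with no recall period. That section points to a data collection sheet that is not part of the text available here and may name the version.
- **Baseline visit.** Procedures lists two visits ahead of the post-injection follow-ups: "Screening: Questionnaires and clinical examination" and "Enrollment: Questionnaire and clinical examination". Neither is called baseline.

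Inclusion criterion 4 requires back pain "with an intensity of at least 4/10 or higher using the Numerical Rating Scale (NRS", without naming a visit or version. The Power Analysis section gives a total of 100 participants and nothing else: no significance level, null rate or target rate. The Study design section includes observational research among its labels.

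**The concern.** A primary outcome should be one quantity that two analysts would compute identically. Here there are two proportions under one label, two candidate pain scores and two candidate baselines, so several different numbers could each be called the primary result. The documents describe no comparison group, so the 2-month responder rate would carry the study's message. The only outside yardstick is in the Introduction, which says that other intradiscal treatments have "50% or less likelihood of reducing pain more than 50" per cent; it speaks to the lower cut-off and has no counterpart at 80%.

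There is also a specific route to bias. If the Screening score both admits patients (at least 4) and serves as baseline, patients caught on a bad day tend to score lower later without any treatment effect, and that fall counts as response. At stake would be an inflated responder rate, or one picked because it looked best.

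**Working it through.** The plan gives no figure to reproduce: 100 participants is stated without inputs. The check therefore asks how far each open choice could move the result. All distributions below are assumptions; only n = 100, the cut-offs and the entry floor of 4 come from the plan.

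**1. The two cut-offs.** Anyone above 80% is also above 50%, so reading the sentence as one joint condition would make the 50% figure redundant. The sensible reading is two separate proportions. Simulation assumptions: true mean NRS 5.5, between-patient SD 1.6, measurement SD 1.0 or 1.5, mean reduction 30% or 45% with SD 0.2 to 0.4, whole-number scores. The >50% rate is then about 20% to 42%, the >80% rate about 3% to 22%, and the gap 16 to 28 points. That gap is the distance between two labelled results. It is not bias, and it misleads nobody when both are shown.

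**2. Error rate, if tests were added.** The plan states no test level for this outcome. Suppose each proportion were tested one-sided at 0.05 by an exact single-arm test at n = 100. The upper bound on any false success is 0.05 + 0.05 = 0.10. Because the events are nested, the chance is lower: about 0.065, 0.065 and 0.076 for assumed null rates (>50%, >80%) of (30%, 10%), (40%, 20%) and (50%, 25%). With no test specified, this inflation is hypothetical.

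**3. Baseline visit.** Individual patients can switch status: a follow-up score of 3 is a 57% reduction from 7, but exactly 50% from 6, which does not exceed 50%.

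For the group, suppose entry requires a rounded Screening score of 4 or more, that is, a value above 3.5. With measurement SD 1.0:

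- total SD = √(1.6² + 1.0²) = 1.887
- z = (5.5 − 3.5)/1.887 = 1.06
- selection raises the mean Screening score by 1.887 × φ(1.06)/Φ(1.06) = 1.887 × 0.2275/0.8554 = 0.50
- share due to measurement error = 1.0²/1.887² = 0.281
- expected fall by Enrollment = 0.50 × 0.281 = 0.14 points

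With measurement SD 1.5 the total SD is 2.193, z = 0.912, the rise is 2.193 × 0.2632/0.8191 = 0.705, the share is 0.468 and the fall is 0.33. Simulation with whole-number scoring gives 0.15 and 0.34. In responder terms, Screening instead of Enrollment as baseline adds 1.0 to 3.1 points to the >50% rate (0.7 to 2.2 if the true mean is 6.0) and 0.1 to 0.7 to the >80% rate.

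**4. NRS version.** Assume both versions are recorded and correlate 0.6 to 0.8. Simulation then classifies 17.1% to 35.5% of patients differently at >50%. If neither version favours response, the switches go both ways and largely cancel. With discordant share d, the difference between the two rates has SD of about √(d/n), and its mean absolute size is √(2/π) × √(d/n):

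- d = 0.171: 0.798 × √0.00171 = 0.033, or 3.3 points
- d = 0.355: 0.798 × √0.00355 = 0.048, or 4.8 points

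Always reporting the higher version adds half of that on average, 1.7 to 2.4 points.

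**5. Yardstick.** The 95% half-width is 1.96 × √(p(1 − p)/100): 9.0 points at 30%, 9.6 at 40% and 9.8 at 50%. The shifts in steps 3 and 4 are at most about half of that.

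**The case for a change.** The strongest case for a change is that the silence is real and cheap to end. Nothing in the text ranks the thresholds, names the version or names the baseline, and a sentence or two would do all three. In a study with no described control, a result that depends on such choices is weaker than one that does not, and sampling error does not excuse an avoidable shift in one direction. Reporting both proportions limits selective emphasis but does not abolish it.

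Much of that stands as a remark on drafting. It does not show that the plan as written yields an unsound answer. The regression-to-the-mean argument needs a rule the plan never states, namely that the Screening questionnaire decides entry and is also the baseline. Participant Recruitment has eligibility reviewed at first contact, before consent, so the qualifying score may come from neither visit. The missing sheet may settle the version. Choosing 50% over 80%, or last-week average over current pain, would be a preference: the plan lists 80% first, and the Introduction's figure describes other treatments, rests largely on uncontrolled or case-control data by its own account, and is never offered as this study's comparator.

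**Conclusion.** No change to the plan follows. The observation is correct as a description: two unranked proportions, an unnamed NRS version and an unnamed baseline visit. It is a gap in detail that an analyst fills sensibly by reporting both named proportions from a pre-injection back pain score and saying which score was used. The plan sets no hypothesis or success criterion for this outcome, so ranking the cut-offs would have no error rate to control.

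The remaining effects are 1.0 to 3.1 points on the >50% rate for the baseline visit, under an entry rule the plan does not state, and 3.3 to 4.8 points of undirected difference for the NRS version, against a half-width of 9 to 10 points. These sizes rest on assumed means, SDs, correlations and treatment effects, on both versions being recorded, and on no loss to follow-up. The judgement would differ if the study were to declare success on whichever proportion passed, or if the Screening score were shown to serve as both entry test and baseline.

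### The responder definitions take no account of treatment added after PRP, and no listed data item would identify later spinal injections or date later surgery

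*Combined protocol and SAP*

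**What the plan says.** **Design.** The Objectives concern changes in "patients with discogenic low back pain after an intradiscal injection of PRP". The Study design section lists "Observational research", and Power Analysis gives "Size of study groups: 100 total participants". The Statistical analysis section names between-group tests and refers to two techniques, but no second group or technique is described anywhere.

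**Outcomes.** In the Data Analysis Plan the primary outcome is "the proportion of participants with >80% and >50% reduction in back pain on the NRS pain score at the 2-month follow-up assessment". The secondary responder outcomes include "the proportion of patients with 30% or greater improvement on the ODI" (no time point given) and a PGIC score below 3. None of these carries a condition on other treatment. MQS III change and daily morphine equivalents are separate secondary outcomes, and so is "the proportion of participants who undergo surgical spine surgery in the study period". None of them is linked to pain or ODI response.

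**Data.** The Procedures section lists "Questionnaires: Demographics, medication use (MSQ III), ODI, PROMIS PF CAT" among the visit questionnaires, and Data Collection adds daily opioid use in morphine equivalents. Neither list has an item for a later spinal injection, or for spine surgery and its date.

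**Other care.** The Exclusion criteria limit recent spinal steroid injection, intradiscal injection, lumbar surgery and opioid use at entry. No section sets an equivalent rule for follow-up. Risks/Benefits says "The patients will be presented with the same options of treatment whether they enroll in the study or decide not to".

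**The concern.** If the score alone decides response, a patient whose opioid use rises after PRP, or who has an epidural steroid injection at week 5, and whose back pain then halves by month 2 is a responder. A patient who has a fusion at month 8 and whose ODI then improves by 30% could count both as an ODI responder and as a surgery case.

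In a randomised comparison, added treatment would occur in both arms and the contrast would still have a meaning. Here there is no second arm, so the proportion describes PRP plus everything that followed it. A reader is likely to take it as a PRP response rate, the more so because the Introduction describes competing intradiscal treatments by their chance of reducing pain by more than half.

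The data gap makes this worse. An analyst who later wished to separate these patients could do so for medication, but not, from the listed items, for injections.

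**Working it through.** The plan has no figure to reproduce on this point. The 100 under Power Analysis comes without a response rate, alpha, power or dropout, and the argument does not depend on how it was reached.

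**Step 1: which added treatments can be identified from the listed data?**

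| Added treatment | Listed follow-up data | Identifiable? |
|---|---|---|
| More analgesics or opioids | MQS III, daily morphine equivalents | Yes |
| Later spinal or repeat intradiscal injection | None | No |
| Spine surgery | Proportion is reported, but no item or date is listed | Not from the lists |

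**Step 2: which outcomes does it reach?** The NRS primary is fixed at 2 months, so medication and injections are the main issue there. Surgery matters mainly for the ODI and for visits later in the 36-month schedule.

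**Step 3: size.** Let q be the share with added treatment before the visit, r0 the response rate in the others, and r1 the response rate in those with added treatment.

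- Score-only rate = (1 - q) x r0 + q x r1
- Rate with added treatment counted as non-response = (1 - q) x r0
- Gap = q x r1

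The documents give no q, so 10% to 30% is an assumption. For r1, 30% to 50% is also assumed. The upper end follows the Introduction, which puts success after epidural steroid injection or surgery at no more than 50%, without defining success and without covering analgesics.

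- Low: 0.10 x 0.30 = 0.03, or 3 points
- High: 0.30 x 0.50 = 0.15, or 15 points
- 95% half-width for a 50% rate at n = 100: 1.96 x sqrt(0.5 x 0.5 / 100) = 0.098, or 9.8 points

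Worked case with r0 = 40%, q = 20%, r1 = 50% (all assumed):

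- Score-only: 0.80 x 0.40 + 0.20 x 0.50 = 42% (Wilson 95% interval 32.8% to 51.8%)
- Added treatment as non-response: 0.80 x 0.40 = 32% (23.7% to 41.7%)

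**Step 4: is the gap the bias?** No. If a fraction r0' of the patients with added treatment would have met the threshold without it, the excess due to that treatment is q x (r1 - r0'), which cannot exceed q x r1. With r0' assumed at 10% to 20%:

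- Low: 0.10 x (0.30 - 0.20) = 1 point
- High: 0.30 x (0.50 - 0.10) = 12 points

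**Step 5: the >80% threshold.** The documents give no rate for it. For any group, r1 at >80% cannot be higher than at >50%, so the gap at >80% is no larger than the gap at >50%.

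**The case against.** The strongest reply is that this is an observational study with standard-of-care visits, whose stated aim is change after PRP. Counting outcomes regardless of other treatment is a legitimate choice for such a study. The attribution problem comes mainly from having no comparator. Scoring added treatment as failure leaves regression to the mean from the NRS entry threshold, natural recovery and placebo response untouched. All of this stands. It is why the score-only rate should be kept and labelled rather than replaced. What it does not answer is that the plan never states this choice and does not list the data needed to examine it.

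A reader might infer several stronger claims that the documents do not support:

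- *The plan provides for open rescue treatment.* The Risks/Benefits sentence says that enrolment does not alter what patients are offered. It is not a rescue rule. The point rests on the plan's silence about follow-up.
- *Patients with added treatment cannot be separated at all.* Medication increases can be. The gap concerns injections, and surgery with its date. The protocol also refers to a data collection sheet that is not among the documents, so an item may exist there.
- *The whole 3 to 15 points is inflation.* It is the fall from rescoring these patients, and so an upper bound on bias (step 4).
- *The primary result becomes more biased out to 36 months.* The primary is measured at 2 months. Accumulating treatment affects later and secondary outcomes.

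**Conclusion.** The concern holds in this form: the NRS, ODI and PGIC responders are defined on scores alone, treatment added after PRP is neither restricted nor accounted for, and with one cohort the resulting rate is response after PRP with any added care. Later spinal injections could not be identified from the listed data.

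Counting added treatment as non-response would lower the rate by 3 to 15 points under assumed inputs (q 10-30%, r1 30-50%). The definition alone could therefore matter as much as sampling error at n = 100. The true bias is smaller than this to the extent that these patients would have responded anyway, and its size cannot be found from the documents. The finding does not show that the primary definition is wrong. It shows that the plan should state what that definition measures and should collect what is needed to check it.

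**What to change.** 1. **Follow-up form.** At each visit add one item: any spinal injection or spine surgery since the last visit, with type, level and date.
2. **Data Analysis Plan.** State that the score-only rate counts outcomes regardless of added treatment. Beside it, pre-specify a second responder rate for NRS, ODI and PGIC at each reported visit. In that rate, a patient with a new lumbar spinal injection, a repeat intradiscal injection or spine surgery before the visit is a non-responder. Apply the same rule to a meaningful rise in analgesic use, for example 6.8 or more MQS III points from baseline. This mirrors the threshold that the plan already uses for a reduction, so that small changes do not count.
3. **Reporting.** Describe the score-only rate as response after PRP with any added care, not as response attributable to PRP alone.

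The cost is one extra question per visit, a few sentences in the plan, and a second, lower responder rate that may understate response to PRP. The medication data are already planned. The rule should be fixed before the data are analysed. No change to permitted care is proposed.
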